8.3.2 Analysis of Clinically Significant Abnormalities

The number and percentage of subjects with clinically significant abnormal values for laboratory parameters will be summarized. A listing of clinically significant abnormal values will also be presented. Clinical significance will be determined for selected parameters based on the criteria listed below in Table 3.

Table 3: Criteria for clinically significant abnormal laboratory value

Parameter name	Unit	Low	High
Hematology			
White blood cells	x10 ⁹ cells/L	<3.0	>16
Lymphocytes	x10 ⁹ cells/L	<0.8	>12
Neutrophils	x10 ⁹ cells/L	<1.5	>13.5
Monocytes	x10 ⁹ cells/L	N/A	>2.5
Eosinophils	x10 ⁹ cells/L	N/A	>1.6
Basophils	x10 ⁹ cells/L	N/A	>1.6
Red blood cells (RBC)	x10 ¹² cells/L	≤ 3.5	≥ 6.4
Hemoglobin - Females - Males	g/L	≤ 95	≥ 175
		≤ 115	≥ 190
Hematocrit - Females - Males	%	≤ 32	≥ 54
		≤ 37	≥ 60
Platelet count	x10 ⁹ cells/L	≤ 75	≥ 700
Blood Chemistry			

Parameter name	Unit	Low	High
Alanine aminotransferase (ALT)		N/A	> 3 x ULN
Aspartate aminotransferase (AST)		N/A	> 3 x ULN
Alkaline phosphatase (ALP)		N/A	>3 x ULN
Total bilirubin		N/A	>2 x ULN
Blood urea nitrogen (BUN)		N/A	≥10.7 mmol/L
Creatinine		N/A	≥176.8 umol/L
Sodium	mmol/L	≤ 126	≥ 156
Potassium	mmol/L	≤ 3	≥ 6
Chloride	mmol/L	≤ 90	≥ 118
Bicarbonate	mmol/L	≤ 16	≥ 35
Glucose (non-fasting)	mmol/L	≤ 2.2	≥ 9.7
HbA1C	%	N/A	≥ 6.5%
Calcium	mmol/L	≤ 2	≥ 3
Phosphorus	mmol/L	≤ 0.5491	≥ 1.7119
Albumin	g/L	≤ 25	≥ 100
Total protein	g/L	≤ 45	≥ 100

8.4 Vital Signs

Vital sign parameters include oral temperature, systolic blood pressure, diastolic blood pressure, pulse rate, respiration rate and weight. Subjects evaluated will be safety subjects with a baseline and at least one post-baseline assessment for that vital sign. The descriptive statistics for actual values and change from baseline will be summarized at each visit. Plots of mean vital sign values over time will be provided.

The analysis of vital signs will also focus on the incidence of clinically relevant outliers based on the following criteria. The incidence as described in [Section 8.2](#) and percentage of clinically relevant outliers determined by each criterion will be summarized. A listing of all vital sign values will be presented for subjects with any vital sign abnormalities. Clinically relevant abnormal vital signs will be flagged in the listing.

Vital Sign	Criteria to determine clinically relevant abnormal vital signs
Temperature	>38°C and an increase from pre-dose of at least 1°C
Pulse	>100 beat per minute (bpm) and an increase from baseline of more than 20 bpm, or <50 bpm and a decrease from baseline of more than 20 bpm.
Systolic Blood Pressure	>160 mmHg and an increase from baseline of more than 40 mmHg, or <90 mmHg and a decrease from baseline of more than 30 mmHg

Diastolic Blood Pressure	>100 mmHg and an increase from pre-dose of more than 30 mmHg, or <45 mmHg and a decrease from pre-dose of more than 20 mmHg
--------------------------	--

8.5 Electrocardiogram (ECG)

The ECG data will be obtained directly from the 12-lead ECG traces. These data include the PR interval (milliseconds), QTcB interval (milliseconds), QRS duration (milliseconds), and heart rate (beats/min).

Descriptive statistics will be used to summarize ECG measurements at each visit for each treatment group. Individual subject listings of ECG parameters at each timepoint will also be provided by treatment group.

A shift table of ECG interpretation results (i.e. normal; abnormal, not adverse event; abnormal, adverse event from baseline to post-baseline) will be presented at each visit by treatment group. If there is no ECG result at baseline, the subject will be counted in the unknown category. A shift to abnormal will include a shift from “unknown” or “normal” at baseline to “abnormal” post-baseline.

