
To assess additional PFT findings in subjects who receive BG00011 compared with placebo.
	
 • Change in absolute and percent predicted FVC from baseline over time. • Carbon monoxide diffusion capacity (DL_{co}), absolute and percent predicted changes from baseline over time. • Total lung capacity, as measured by plethysmography, absolute and percent predicted changes from baseline over time.

To assess performance on the 6MWT in subjects who receive BG00011 compared with placebo.
	
Change from baseline in 6MWT parameters at Weeks 26 and 52.

To evaluate the safety and tolerability of BG00011.
	
 • The incidence, severity, outcome, and relationship to study treatment of AEs and SAEs. • Change from baseline in clinical laboratory test results, vital signs, ECG, PFT results, and HRCT findings. • Immunogenicity (antibodies to BG00011).

To evaluate the serum concentration of BG00011.
	
Measurement of BG00011 serum concentrations using sparse PK sample collection at select timepoints during the study.

Exploratory Objectives
	
Exploratory Endpoints

████████████████████ ████████████████████████████████ ████████████████████████████████
	
██████████████████████████████ ████████████████████████████████

██ ████████████████████████████████
	
██ ████████████████████████████████ ████████████████████████████

[REDACTED]
	
[REDACTED]
 
• [REDACTED]• [REDACTED]• [REDACTED]

[REDACTED]
	
[REDACTED]

[REDACTED]
	
• [REDACTED]• [REDACTED]• [REDACTED]

[REDACTED]
	
• [REDACTED]• [REDACTED]• [REDACTED]

[REDACTED]
	
• [REDACTED]

[figure not shown]

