6.1 General Consideration

Data listings will be provided by treatment group, subjects and visits, if applicable. Summary statistics and statistical analyses will only be presented for data where detailed in this SAP and will generally only be performed for subjects included in the relevant analysis population. Unless otherwise specified, all variables will be summarized for the MITT population.

Summary statistics will be presented throughout for all endpoints at all visits including follow-up visits. For continuous variables, summary statistics will generally include number of subjects with data, mean, standard deviation (SD), median, minimum and maximum. In addition, the 95% confidence interval (CI) for the mean will be presented. For log-normal data the geometric mean and geometric coefficient of variation (CV) will also be presented. For categorical endpoints, summary statistics will generally include number and percentage of subjects with data in each category.

The statistical software, SAS®, will be used for all summaries and statistical analyses.

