8.3 Analysis of Laboratory Tests

The following laboratory safety assessments will be conducted:

- Hematology: complete blood count (CBC) including red blood cell count, white blood cell counts with differentials (neutrophils, lymphocytes, monocytes, eosinophils, and basophils), hemoglobin, hematocrit, mean corpuscular volume (MCV), mean corpuscular hemoglobin (MCH), and mean corpuscular hemoglobin concentration (MCHC).
- Serum chemistry: albumin, alkaline phosphatase, alanine aminotransferase (ALT), aspartate aminotransferase (AST), blood urea nitrogen (BUN), calcium, chloride, carbon dioxide, creatinine, direct bilirubin, gamma-glutamyl transpeptidase, glucose, lactate dehydrogenase (LDH), phosphorus, potassium, sodium, total bilirubin, total protein
- Urinalysis: including urine protein, glucose, ketones, occult blood, and white blood cells by dipstick, with microscopic examination if indicated

The clinical laboratory parameters include safety assessment listed above will be summarized by treatment group and visit. Descriptive statistics will be presented for continuous variables at each visit by treatment group, including number of subjects, mean, standard deviation, median, 25%, 75% quartiles, minimum, and maximum values. Plots of mean value with standard error for numeric laboratory parameters at each visit will be presented. For categorical endpoints, summary statistics will be presented at each visit by treatment group include number and percentage of subjects with data in each category.

Changes from baseline and percent changes from baseline in quantitative laboratory values will be summarized using descriptive statistics by treatment group and visit.

The clinical laboratory parameters by worst post-baseline grade will be provided for all safety assessment. The worst post-baseline cumulative grade will be provided for the safety assessments for Hematology and Urinalysis.

Individual subject listings of clinical laboratory parameters at each visit will be provided. Values for hematology, serum chemistry, and urinalysis values outside the central laboratory reference ranges will be flagged on the individual subject data listings.

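### SAP 8.5 does not specify numeric change from baseline for the ECG parameters and names only the rate-sensitive QTcB: a minor gap that is cheap to close

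*SAP*

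**What the plan says.** SAP 2 includes this among the secondary safety endpoints: "Change from baseline in clinical laboratory test results, vital signs, ECG, PFT results, and HRCT findings".

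For two of those items the SAP then plans the matching numeric analysis. On laboratory tests, 8.3 says: "Changes from baseline and percent changes from baseline in quantitative laboratory values will be summarized using descriptive statistics by treatment group and visit". On vital signs, 8.4 says: "The descriptive statistics for actual values and change from baseline will be summarized at each visit".

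For ECG, 8.5 names the variables ("These data include the PR interval (milliseconds), QTcB interval (milliseconds), QRS duration (milliseconds), and heart rate (beats/min") and gives one sentence on their numeric summary: "Descriptive statistics will be used to summarize ECG measurements at each visit for each treatment group". Change from baseline is not mentioned. The section adds individual listings and, by visit and arm, one output that refers to baseline: "A shift table of ECG interpretation results (i.e. normal; abnormal, not adverse event; abnormal, adverse event from baseline to post-baseline) will be presented".

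Two general sentences in SAP 6.1 bear on how the silence should be read, and they pull in different directions: "Summary statistics will be presented throughout for all endpoints at all visits including follow-up visits" and "Summary statistics and statistical analyses will only be presented for data where detailed in this SAP".

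Protocol 16.6.2.4 says only that ECG changes from baseline may be summarized. SAP 1 states that the SAP supersedes the protocol's statistical considerations and that safety data will be analyzed in full despite early termination.

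**The concern.** A programmer who follows 8.5 literally would produce means of PR, QRS, QTcB and heart rate at each visit. Nothing would show how far each subject moved from his or her own starting value. After baseline, the protocol's Schedule of Events (5.2) has scheduled ECGs only at Weeks 26, 52 and 60, and the trial stopped early. The baseline mean therefore covers nearly everyone and each later mean covers a smaller set. Subtracting one from the other does not give the mean within-subject change.

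PR has some standing here. Protocol 4.4.3 reports that two of the four Phase 2a BG00011 subjects with serious adverse events had atrioventricular block, one of them Type II second-degree. Investigators judged none of these events related, and Protocol 4.4.2.2 reports no treatment-related ECG changes in monkeys. So this is a reason to tabulate the interval change, not evidence of an effect.

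The second strand is the QT correction. Bazett's formula divides QT by the square root of RR. If the true dependence of QT on RR is weaker than that, QTcB rises with heart rate even when repolarization is unaffected. An arm difference in heart rate would then be mixed into the only QT comparison in the tables.

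**Working it through.** **Is numeric change from baseline specified?** The documents give no ECG figure to reproduce, so the check is a comparison of sections.

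- Endpoint (SAP 2): change from baseline in laboratory tests, vital signs and ECG.
- Laboratory tests (8.3): by-visit values, change and percent change.
- Vital signs (8.4): actual values and change, for safety subjects with a baseline and at least one post-baseline value.
- ECG (8.5): by-visit values only, with no such condition on the subjects, plus a categorical shift table.

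The shift table has three categories: normal, abnormal without an adverse event, and abnormal with one. A subject read as normal both times falls in the same cell whether PR has moved a little or a lot. A shift to abnormal is defined as starting from normal or unknown, so lengthening in a subject already abnormal at baseline does not count as one. The table is referenced to baseline but carries no interval information.

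**How rate-sensitive is QTcB?** The formulas, QT levels and heart rates below are assumptions; none is in the documents.

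Let RR = 60/HR in seconds, QTcB = QT/RR^(1/2) and QTcF = QT/RR^(1/3). Suppose there is no drug effect and QT = 410 × RR^p ms. Then

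- QTcB = 410 × RR^(p − 1/2)
- QTcF = 410 × RR^(p − 1/3)

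For p = 1/3, QTcB = 410 × (HR/60)^(1/6), which is 420.7 ms at 70 bpm and 430.1 ms at 80 bpm. The rise is 9.5 ms before rounding. For p = 0.4, it is 410 × [(80/60)^0.1 − (70/60)^0.1] = 5.6 ms. For 70 to 80 bpm:

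| True power p | Change in QTcB | Change in QTcF |
|---|---|---|
| 1/3 | +9.5 ms | 0 |
| 0.4 | +5.6 ms | −3.6 ms |
| 0.5 | 0 | −8.8 ms |

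At p = 1/3, with QTcF equal in both arms at 400 to 430 ms and a reference rate of 65 to 80 bpm, the apparent QTcB difference is:

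- +2 bpm: +1.7 to +2.2 ms
- +5 bpm: +4.3 ms (400 ms, from 80 bpm) to +5.4 ms (430 ms, from 65 bpm)
- +10 bpm: +8.3 to +10.5 ms
- −5 bpm: −4.5 to −5.8 ms

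**Can QTcF be had from what is collected?** Since QT = QTcB × RR^(1/2), QTcF = QTcB × RR^(1/6) = QTcB × (60/HR)^(1/6). For example, QTcB 420 ms at 70 bpm gives QT = 420 × (60/70)^(1/2) = 388.8 ms and QTcF = 409.3 ms. Both inputs are listed in 8.5. The conversion must be made ECG by ECG, not on visit means.

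**The case against.** A reader might infer that the ECG endpoint is never analyzed. The documents do not support that. The shift table is a change from baseline in ECG, in categorical form, and SAP 2 does not say that the change must be reported interval by interval. SAP 6.1 promises summaries for all endpoints, which can be read to cover this one. SAP 1.2 places the detailed table layouts in shells that are not among the documents reviewed. The protocol made the numeric summary optional. What stands is narrower: 8.5 does not specify it, where 8.3 and 8.4 do.

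A reader might also infer that a heart-rate difference will show up as a QT effect. That is conditional twice over, on a heart-rate difference and on a power below 0.5. No document reports such a difference. The Phase 2a counts of dyspnea (5) and hypoxia (4) in BG00011 subjects come without placebo counts or heart-rate data, and Protocol 4.4.3 describes vital-sign changes at doses up to 1.0 mg/kg as comparable to those expected in IPF. Heart rate is summarized beside QTcB, pulse gets change from baseline and outlier criteria in 8.4, and 8.1 rules out testing on safety data, so no p-value would turn an artefact into a signal. In addition, the word *include* does not close the variable list in 8.5.

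Nor is QTcF simply the correct choice. By the table above it errs in the other direction once the power exceeds 1/3. That is a reason to show both corrections, not to replace one with the other.

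Finally, change from baseline does not cure attrition. It makes each visit's figure a within-subject quantity, but it says nothing about subjects with no ECG at that visit.

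**Conclusion.** The point holds as a minor one and a cheap improvement. Section 8.5 leaves the numeric part of a stated secondary safety endpoint unspecified for PR, QRS, QTc and heart rate, and the shift table of the overall reading does not fill that gap. This conclusion rests on the SAP text alone; the table shells might already contain the missing columns.

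The QTcB strand is a conditional sensitivity: at a power of 1/3, roughly 0.9 to 1.1 ms of apparent QTcB difference per bpm of arm difference in heart rate, falling to nothing at 0.5. It rests on the assumed QT levels, heart rates and powers shown, and is not a prediction for this trial. The documents do not support a claim that the endpoint goes unanalyzed or that a spurious QT effect should be expected.

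**What to change.** Make two changes in SAP 8.5.

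1. Replace the sentence on descriptive statistics with wording such as: *Actual values and change from baseline in PR, QRS, QTc and heart rate will be summarized at each visit by treatment group, for safety subjects with a baseline and at least one post-baseline ECG.* This follows 8.4.
2. Add QTcF = QTcB × (60/HR)^(1/6), computed for each ECG, and report it alongside QTcB. If the two disagree, read both against the heart-rate summary.

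The cost is two sentences, one derived variable and a few extra table columns. No new ECGs or readings are needed. SAP 1.1 already provides for a documented new version if a change is made after finalization.

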8.6 Physical Examination

Abnormal findings which are noted after subjects received study treatment and are deemed by the investigator as clinically significant will be reported as AEs and included in AE analyses.

8.7 Immunogenicity (Anti-BG00011 Antibodies)

Blood samples for the presence and titer of anti-BG00011 antibodies will be collected at scheduled visits of baseline, weeks 4, 12, 26, 38 and 60 (safety follow-up). The analysis visit should be defined using window in the table below in Table 4. Each blood sample will initially be tested for the presence of anti-BG00011 antibodies using a validated electrochemiluminescence (ECL) method. Confirmed positive samples using the screening assay will be titered and subsequently tested using a validated neutralization assay.

Table 4: Visit Windows for Anti-BG00011 Antibodies

Analysis Visit	Target visit day	Analysis visit window
Baseline (Day 0)	1	Most recent non-missing pre-dose value
Week 4	29	[2,57]
Week 12	85	[58,134]
Week 26	183	[135,225]
Week 38	267	[226,344]

Safety Follow-up (Week 60)	421	
 • If subject who discontinued treatment due to reasons other than study termination by sponsor: > min (393, study day of each subject's week 52/EOT visit in treatment period) * • If subject who discontinued treatment due to study early termination by sponsor: > min (393, study day of each subject's last dose)
-------------------------------	-----	---

* For subjects who discontinued the treatment due to reasons other than study termination by sponsor will go on to complete all scheduled visits until either week 52 or the study was terminated by sponsor due to the urgent safety measure whichever occurs first. The Week 52/EOT visit in treatment period is defined as the last visit scheduled for either week 52 or study termination due to the urgent safety measure.

Antibody results will be presented by treatment group and subject in listings. The incidence of antibodies to BG00011 will be summarized over time by treatment group using descriptive statistics.

Since the study early termination, the antibody results will not be included in the Part 1 data of the two-part database lock. The antibody data will be included in the Part 2 data. In order to keep the data integrity, the reconciliation of the antibody samples will be conducted prior to the Part 1 data being cleaned and finalized.

9 Pharmacokinetics (PK) Analysis

BG00011 concentrations in serum will be summarized for PK population using descriptive statistics at the scheduled PK sample collection visits. Number of evaluable subjects, arithmetic mean, standard deviation, median, 25% and 75% quartiles, minimum, maximum, geometric mean, and CV will be presented at each visit.

This study will collect only sparse PK samples; thus, no noncompartmental or compartmental methods will be used to analyze the PK data for presentation in the clinical study report. The mean serum concentrations (+/- SD) will be plotted over time by treatment group on the linear and log linear scale.

No dose-proportionality assessments will be conducted because of the sparse PK data sampling. Atypical drug concentrations (e.g., very low or very high) will be excluded from the analysis, if no apparent explanation exists. Concentration observations will also be removed from the data set if corresponding dosing or sampling times are missing or cannot be reconstructed. Measurements that are below the level of quantification (BLQ) will be set to missing and removed from analysis before statistics are calculated, if the BLQ occurs before the first measurable concentration (such as pre-dose), it should be set to zero. If the value of the concentration is "Non-Determinable", then the concentration value will be set to missing.

A listing of individual serum concentration data will be provided. The BLQ and all atypical drug concentration excluded from the analysis will be flagged in the listing.

[REDACTED]

[REDACTED]

[REDACTED]

[REDACTED]

[Redacted]

[Redacted]

[Redacted]

11 Reference

Berry, J. D., Miller, R., Moore, D. H., Cudkowicz, M. E., Van Den Berg, L. H., Kerr, D. A., Dong, Y., Ingersoll, E. W., and Archibald, D. The combined assessment of function and survival (CAFS): A new endpoint for ALS clinical trials. *Amyotrophic Lateral Sclerosis and Frontotemporal Degeneration*. 2013; 14(3):162-168.

[REDACTED]

ICH E9 (R1): Addendum to statistical principles for clinical trials on choosing appropriate estimands and defining sensitivity analyses in clinical trials. Endorsed by the ICH Steering Committee. 2014.

ICH E9 (R1): Addendum on Estimands and Sensitivity Analysis in Clinical Trials to the Guideline on Statistical Principles for Clinical Trials. European Medicines Agency. 2017.

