The study was monitored by an independent data safety monitoring board (DSMB) and included safety evaluations that would enable detection of respiratory events (e.g., IPF exacerbation; changes in lung function, including decreases from baseline in FVC by $\geq 12\%$, total lung capacity by $\geq 8\%$, and diffusing capacity of the lungs for carbon monoxide [DL_{CO}] by $\geq 15\%$). Four cohorts completed dosing through 1.0 mg/kg. Prior to the completion of dosing in the fifth and highest dosing cohort (3.0 mg/kg), the study was stopped after meeting the prespecified protocol stopping

CONFIDENTIAL

The information contained herein may not be used, disclosed, or published without the written consent of Biogen MA Inc.

criteria, when 2 subjects experienced clinically significant sustained decreases from baseline respiratory status. Following the decision to stop the 3.0 mg/kg cohort and additional discussions with the DSMB, Biogen conducted a detailed analysis of the available PK, PD, and safety data from all cohorts and concluded that the potential benefit/risk of BG00011 was acceptable for dosing patients with IPF, with appropriate safety monitoring, at doses not exceeding 1.0 mg/kg. A summary of the PK, PD, and safety data for Study 203PF201 is as follows.

Pharmacokinetic data show that after repeated weekly SC administration, BG00011 exposure increased approximately proportionally to doses ranging from 0.015 to 1.0 mg/kg, but increased greater than proportionally at doses >1.0 mg/kg. After the last dose, the mean terminal $t_{1/2}$ of BG00011 ranged from 168 to 211 hours across the dose range (approximately 174 hours following repeated administration at doses <3.0 mg/kg). Serum concentrations were relatively sustained throughout the 168-hour sampling period, with the time to reach maximum observed concentration (T_{max}) after the last dose occurring at 24 to 48 hours.

In this study, BG00011 decreased the level of phosphorylated SMAD2 (pSMAD2) in BAL cells starting at the 0.3 mg/kg dose and achieved $\geq 70\%$ reduction at the 1.0 mg/kg dose. In addition, a substantial decrease in gene expression of several prespecified genes linked to TGF- β signaling was also observed between the 0.3 and 1.0 mg/kg doses. These decreases in pSMAD and gene expression established proof of biology.

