10. DISCONTINUATION OF STUDY TREATMENT AND WITHDRAWAL OF SUBJECTS FROM THE STUDY

10.1. Discontinuation of Study Treatment

Study treatment discontinuation is defined as the premature ending of study treatment dosing, i.e., when a subject permanently stops taking the study treatment before the last dose (the Week 51 dose). Reasons for mandatory study treatment discontinuation are listed in Section 10.1.1. The primary reason for study treatment discontinuation must be recorded in the subject's CRF.

Subjects who discontinue study treatment must return for an End of Treatment Visit as soon as possible, but within 4 weeks after discontinuation of treatment. All assessments planned for the Week 52 Visit except the HRCT scan will be performed. If the End of Treatment Visit occurs in the visit window for the next scheduled visit, then the scheduled visit may serve as the End of Treatment Visit, and all assessments for the End of Treatment Visit should occur at that time. Subjects will go on to complete all remaining visits as scheduled, including the Week 52 and Safety Follow-Up Visits (see Table 2 for a list of assessments to occur at the End of Treatment and Safety Follow-Up Visits).

Note: A subject who misses 1 or more doses of study treatment should restart study treatment, receive all remaining doses, and complete all remaining study visits.

See Section 10.2 for information related to the withdrawal of subjects from study.

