5.4 Pharmacokinetic (PK) population

The pharmacokinetic (PK) population will include all safety subjects who have at least one PK concentration measurement. Subjects will be analyzed by the actual treatment received.

6 General Analysis

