6.1.1.2 Analysis Visit

Observations that are collected after the first randomized dose as scheduled visit will be used to the corresponding analysis week.

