6.1.1.4 Early Termination or Unscheduled Visits for Acute Exacerbation of IPF

In general, when data are summarized by analysis visit, the Early Termination Visit or Unscheduled Visits for Acute Exacerbation of IPF will be assigned to an appropriate scheduled analysis visit by using a window scheme provided in Table 1.

Table 1: Visit Windows for Early Termination or Unscheduled Visits

Scheduled Visit Time	Target study day	Analysis visit window (days)	
		Efficacy & Safety Data	PK Data
Baseline (Day 0)	1	Most recent non-missing value on/before the date of first dose	
Day 5*	6	N/A	[6,7]
Week 4	29	[2,43]	[8,43]
Week 8	57	[44,71]	
Week 12	85	[72,99]	
Week 16	113	[100,127]	
Week 20	141	[128,162]	
Week 26	183	[163,203]	
Week 32	225	[204,246]	
Week 38	267	[247,288]	
Week 44	309	[289,337]	
Week 52	365	[338,393]	
Safety Follow-up (Week 60)	421	
 • If subject who discontinued treatment due to reasons other than study termination by sponsor: > min (393, study day of each subject's week 52/EOT visit in treatment period) ** • If subject who discontinued treatment due to study early termination by sponsor: > min (393, study day of each subject's last dose) 	

*The Day 5 Visit is for blood collection only (for PK analysis) and may be done in the clinic or at home (by appropriate personnel). Sample collection should occur on Day 5 (not sooner), with a +1 day window allowed (i.e., collection should occur on Day 5 but may occur on Day 6).

** For subjects who discontinued the treatment due to reasons other than study termination by sponsor will go on to complete all scheduled visits until either week 52 or the study was terminated by sponsor due to the urgent safety measure whichever occurs first. The Week 52/ EOT visit in treatment period is defined as the last visit scheduled for either week 52 or study termination due to the urgent safety measure.

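### For subjects who stopped treatment for reasons other than sponsor termination, the SAP leaves quantifiable off-drug concentrations in the Week N PK summaries, and Table 1's last-dose rule for sponsor-stopped subjects has no stated precedence

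*SAP*

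**What the plan says.** SAP section 9 (Pharmacokinetics (PK) Analysis) gives the summary rule: "BG00011 concentrations in serum will be summarized for PK population using descriptive statistics at the scheduled PK sample collection visits". SAP section 5.4 defines who enters it: "The pharmacokinetic (PK) population will include all safety subjects who have at least one PK concentration measurement". Neither carries an on-treatment condition.

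Two rules assign samples to weeks:
- **Scheduled visits**, SAP section 6.1.1.2: "Observations that are collected after the first randomized dose as scheduled visit will be used to the corresponding analysis week".
- **Early termination and exacerbation visits**, SAP section 6.1.1.4: these "will be assigned to an appropriate scheduled analysis visit by using a window scheme provided in Table 1". Table 1 has a PK column.

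The Safety Follow-up row of Table 1 separates two groups. For the sponsor-terminated group it reads "If subject who discontinued treatment due to study early termination by sponsor: > min (393, study day of each subject's last dose"). For subjects who stopped for any other reason, the cut-off is the day of the Week 52/EOT visit. The footnote defines that visit as the last one scheduled for Week 52 or for study termination.

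The SAP takes protocol version 1 as its reference. Section 10.1 of that protocol requires an End of Treatment visit within 4 weeks of stopping, with all Week 52 assessments except HRCT, and then: "Subjects will go on to complete all remaining visits as scheduled, including the Week 52 and Safety Follow-Up Visits".

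SAP section 9 removes four kinds of record: atypical values that cannot be explained, records whose dosing or sampling times are missing, values below quantification after the first measurable one, and non-determinable values.

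**The concern.** A subject who stops dosing but keeps attending visits continues to give PK samples, and those samples measure washout. If they carry a Week N label, the Week N mean, geometric mean and mean-over-time plot blend on-drug and off-drug values. The centre is pulled down and the spread widened.

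Serum concentration is a stated secondary endpoint. The trial was stopped on a safety recommendation, and Protocol section 4.5 justified the dose as not exceeding exposures seen at 1.0 mg/kg. A reader of the study report is likely to take the Week N row as exposure during treatment. The primary FVC analysis censors at treatment discontinuation (SAP section 7.2.1), so the PK table would also describe a different set of observations from the efficacy analysis beside it.

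**Working it through.** The plan states no figure on this point, so there is none to reproduce. The check has two parts.

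**1. Tracing the assignment rules (illustrative days)**

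*Stopped for another reason.* Last dose day 120, scheduled Week 26 sample day 183, last scheduled visit day 267.
- Section 6.1.1.2 assigns the sample to Week 26. Day 183 also lies in the Table 1 window [163,203].
- The Safety Follow-up condition is day > min(393, 267) = 267, which day 183 does not meet.
- The sample stays in Week 26, 183 − 120 = 63 days after the last dose.
- Reading Week 52/EOT as the visit held soon after stopping would conflict with the footnote. It would also leave that visit's own sample in Week N, because the condition is strictly greater than.

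*Stopped by the sponsor.* Last dose day 170, early-termination sample day 180.
- Week 26 window: 163 ≤ 180 ≤ 203, met.
- Safety Follow-up: 180 > min(393, 170) = 170, also met.
- Both rows apply and no precedence is stated.

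*Exclusions in SAP section 9.* A low value after dosing stopped has an explanation, so the atypical-value rule does not remove it. The missing-time rule does not apply when dates are known. The quantification rule removes only samples that are no longer measurable.

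**2. Size, if such samples remain quantifiable**

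Inputs:
- Half-life: "approximately 174 hours following repeated administration at doses <3.0 mg/kg" (Protocol section 4.4.3), which is 7.25 days. The range of means is 168 to 211 h.
- Off-drug share f of a visit's values: not in the documents; assumed 5% to 25%. The 15% planning dropout in SAP section 4 is not a treatment-discontinuation rate.
- Further assumptions: mono-exponential decline; on-drug samples at a 7-day trough; every off-drug sample quantifiable.

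Concentration relative to trough, d days after the last dose: r = 2^(−(d − 7)/7.25).
- d = 14: 51%
- d = 28: 13.4%
- d = 42: 3.5%
- d = 63: 0.5%

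Ratio of pooled to on-drug mean: arithmetic 1 − f(1 − r); geometric r^f.

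| Days since last dose | f | Arithmetic | Geometric |
|---|---|---|---|
| 14 | 5% | 0.976 | 0.967 |
| 14 | 15% | 0.927 | 0.904 |
| 14 | 25% | 0.878 | 0.846 |
| 28 | 5% | 0.957 | 0.904 |
| 28 | 15% | 0.870 | 0.740 |
| 28 | 25% | 0.784 | 0.605 |
| 42 | 5% | 0.952 | 0.846 |
| 42 | 15% | 0.855 | 0.605 |
| 42 | 25% | 0.759 | 0.433 |

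Twenty-eight days is the main case because an End of Treatment sample may be taken up to 4 weeks after stopping.

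Sensitivity to half-life at 28 days and f = 25%: r is 0.125 at 168 h and 0.191 at 211 h. The arithmetic ratio is 1 − 0.25 × 0.875 = 0.78 and 1 − 0.25 × 0.809 = 0.80. The geometric ratio is 0.125^0.25 = 0.59 and 0.191^0.25 = 0.66.

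**The case against.** **Table 1 does contain a last-dose rule.** This stands. A reader might infer that the SAP ignores time of last dose altogether, or that the effect is worst where the sponsor stopped many subjects. The documents do not support either reading: for sponsor-terminated subjects Table 1 sends samples after the last dose to Safety Follow-up. What remains for that group is the overlap with the weekly windows.

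**The Safety Follow-up row would mix very different washout times.** This is mostly answered by SAP section 6.1.1.4, which keeps the assessment nearest the target day when a window holds two. The follow-up visit comes 56 days after End of Treatment and the target is day 421, so the follow-up sample is nearer whenever End of Treatment falls before day 421 − 28 = 393. Mixing remains only for subjects without a follow-up sample. That row is off drug in any case and cannot lower a Week N mean.

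**The bias cannot be sized.** This also stands. Fully washed-out samples may fall below quantification and drop out, causing no shift, and no quantification limit or off-drug share is given. The figures above are conditional.

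**By-visit description is all that was promised.** In part. Protocol section 13.2 leaves individual exposure to a population PK model reported separately, and SAP section 9 also gives the median, quartiles and a listing. The median is less sensitive but not immune. If off-drug values are all lower, at f = 25% the pooled median sits at the (0.50 − 0.25)/0.75 = 33rd percentile of the on-drug values.

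**A strict 7-day filter would do harm.** This stands. Protocol section 10.1 tells subjects who miss doses to restart, and a filter on days alone would drop some of their samples although they remain on treatment.

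**Conclusion.** The point holds for subjects who permanently stopped for reasons other than sponsor termination. SAP sections 5.4, 6.1.1.2 and 9, read with Table 1, keep their quantifiable off-drug concentrations in Week N. For sponsor-terminated subjects the defect is narrower: two Table 1 rows can claim the same sample.

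The direction is downward whenever the retained samples are quantifiable. At 28 days, with the 174 h half-life and an assumed off-drug share of 5% to 25%, the loss is about 4% to 22% in the arithmetic mean and 10% to 40% in the geometric mean. A reader might take these as estimates of what the trial's tables will show. They are not, because the share and the quantification limit are unknown.

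Only descriptive PK tables and mean plots are affected. No test and no primary or safety analysis in the SAP uses them. This is a cheap improvement, not a threat to the trial's conclusions.

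**What to change.** In SAP section 9:
- Flag each sample as on or off treatment. For a subject who has not permanently discontinued, treatment-period samples are on treatment, including those after an isolated missed dose. For one who has, samples beyond one dosing interval (7 days, plus a stated tolerance) after the last dose are off treatment. Safety Follow-up samples are off treatment.
- Restrict the by-visit table and mean plots to on-treatment samples.
- Summarise the rest separately by days since last dose, for example up to 7, 8–14, 15–28, 29–56 and more than 56.
- Keep every sample in the listing, with days since last dose and the flag.
- State that, for PK data, the last-dose rule in Table 1 takes precedence over the weekly windows.

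The cost is wording and one derived variable; SAP section 9 already needs dosing and sampling times. Nominal visits will have slightly fewer values. These include the occasional sponsor-stopped subject's sample drawn within a week of the final dose, which the precedence rule moves to Safety Follow-up and the days-since-dose table still shows.
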